4.2.1 Co-primary efficacy endpoints

4.2.1.1 Overall survival

The primary analysis of the co-primary endpoint, OS, will occur when approximately 491 deaths have occurred (approximately 70% maturity). OS will be analysed using a stratified log-rank test adjusting for age at randomisation (<65 vs ≥65 years of age), sex (male vs female), and smoking history (smoker vs non-smoker) for generation of the p-value and using the Breslow approach for handling ties (Breslow, 1974).

The effect of treatment will be estimated by the hazard ratio (HR) together with its corresponding (1-alpha adjusted)% CI and p-value for the ITT population.

The covariates in the statistical modelling will be based on the values entered into IVRS at randomisation, even if it is subsequently discovered that these values were incorrect. In addition a sensitivity analysis will be produced which use the covariates recorded in the CRF.

The HR and CI can be estimated from the stratified log-rank as follows (Berry et al 1991, Collett 2003, Sellke and Siegmund 1983):

$$HR = \exp\left(\frac{U}{V}\right)$$

$$95\% \text{ CI for HR} = \left(\exp\left\{\frac{U}{V} - \frac{1.96}{\sqrt{V}}\right\}, \exp\left\{\frac{U}{V} + \frac{1.96}{\sqrt{V}}\right\} \right)$$

Where $U = \sum_k U_k = \sum_k \sum_i (d_{1ki} - e_{1ki})$ is the stratified log-rank test statistic obtained from the SAS LIFTEST procedure, $\sqrt{V} = \sqrt{\sum_k V_k}$, is its standard deviation, k denotes the stratum and d_{1ki} and e_{1ki} are the observed and expected events in Group 1, stratum k.

Kaplan-Meier plots of OS will be presented by treatment arm. Summaries of the number and percentage of patients who have died, those still in survival follow-up, those lost to follow-up and those who have withdrawn consent will be provided along with the median OS for each treatment. The assumption of proportionality will be assessed.

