 - This will be determined from the centre number (CENTRE). If there are less than 20 events in the “South America” category, these patients will be combined with those in North America.
- Race (White, Black/African-American, Asian, Other [Native Hawaiian/Pacific Islander or American Indian/Alaska Native or Others]).
 - This will be determined from the response to “Race” (DEM module) on the eCRF at screening.
- PD-L1 status (\geq 25% vs <25%).
 - Only samples with sample date on or before first dose should be used

- for multiple evaluable samples with sample date on or before the first dose, the sample with the highest PD-L1 % tumour membrane staining result should be used
- EGFR (positive vs negative)

The subgroup analyses will be based on values recorded on the eCRF.

Other baseline variables may also be assessed if there is clinical justification or an imbalance is observed between the treatment arms. The purpose of the subgroup analyses is to assess the consistency of treatment effect across expected prognostic factors.

No adjustment to the significance level for testing will be made since all these subgroup analyses will be considered exploratory and may only be supportive of the primary analysis of OS.

For each subgroup, the HR and 95% CI will be calculated from an unstratified Cox proportional hazards model with treatment as only covariate. The Cox models will be fitted using SAS® PROC PHREG with the Efron method to control for ties, using the by statement to obtain HR and 95% CI for each subgroup level separately.

These hazard ratios and associated two-sided 95% CIs will be summarised and presented on a forest plot, along with the results of the overall primary analysis.

If there are too few events available for a meaningful analysis of a particular subgroup (it is not considered appropriate to present analyses where there are less than 20 events in a subgroup), the relationship between that subgroup and OS will not be formally analysed. In this case, only descriptive summaries will be provided.

Effect of covariates on the HR estimate

Cox proportional hazards modelling will be employed to assess the effect of covariates on the HR estimate for the primary treatment comparison. A model will be constructed, containing treatment and the stratification factors alone, to ensure any output from the Cox modelling is likely to be consistent with the results of the stratified log-rank test.

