The result from the initial model and the model containing additional covariates will be presented.

Additional covariates for this model will be age at randomization, sex, smoking status, stage of disease at study entry, histology, best response to prior anticancer therapy, WHO performance status, region and race.

The model will include the effect regardless of whether the inclusion of effect significantly improves the fit of the model providing there is enough data to make them meaningful.

Consistency of treatment effect between subgroups

Interactions between treatment and stratification factors will also be tested to rule out any qualitative interaction using the approach of [Gail and Simon 1985](#).

Impact of switching (crossover outside of this study) to immunotherapies (or other potentially active investigational agents) on OS analyses

Exploratory analyses of OS adjusting for the impact of subsequent immunotherapy or other treatment may be performed, if a sufficient proportion of patients switch.

Methods such as Inverse Probability of Censoring Weighting ([Robins 1993](#)), Rank Preserving Structural Failure Time ([Robins and Tsiatis 1991](#)), and other methods in development will be explored as appropriate. The decision to adjust and the final choice of methods will be based on a blinded review of the data and the plausibility of the underlying assumptions. Additional supportive analysis by censoring the treatments switchers at the time of initiation of subsequent therapy will also be conducted. These analyses are intended to further support the OS benefit and reimbursement appraisals.

Baseline and time-dependent characteristics will be explored, and summaries of baseline characteristics will be provided by treatment arm, splitting between those that have and haven't switched at the time of the analyses.

Subsequent therapies received after discontinuation of treatment will be summarised and listed by treatment group. Patients who subsequently received an immunotherapy agent or entered an immunotherapy trial will be summarised and listed by treatment arm according to line of subsequent therapy, i.e. immediately after immunotherapy or as a later line.

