4.2.1.2 Progression free survival

PFS based upon the programmatically derived RECIST outcome using the BICR data (including all scans regardless of whether they were scheduled or not) will be analysed by stratified log-rank tests, the same methodology as described for the OS analyses.

The primary analysis of the co-primary endpoint, PFS, will occur when it is expected that 458 PFS events have occurred (65% maturity). PFS based upon the BICR data will be analyzed using a stratified log-rank test adjusting for the same factors as for OS. The effect of treatment will be estimated by the HR together with its corresponding (1-alpha adjusted)% CI and p-value for the full ITT population. Kaplan-Meier plots of PFS will be presented by treatment arm. Summaries of the number and percentage of patients experiencing a PFS event, and the type of event (RECIST 1.1 or death) will be provided along with median PFS for each treatment.

The assumption of proportionality will be assessed in the same way as for OS. The analysis will be based on the programmatically derived PFS using BICR data.

Supportive summaries/graphs

The treatment status at progression of patients at the time of analysis will be summarised. This will include the number (%) of patients who were on treatment at the time of progression,

the number (%) of patients who discontinued study treatment prior to progression, the number (%) of patients who have not progressed and were on treatment or discontinued treatment. This will also provide distribution of number of days prior to progression for the patients who have discontinued treatment.

The number of patients prematurely censored will be summarised by treatment arm. A patient would be defined as prematurely censored if they had not progressed (or died in the absence of progression) and the latest scan prior to DCO was more than one scheduled tumour assessment interval plus 2 weeks (10 weeks if time period between randomisation and DCO for that patient is 48 weeks or less; 14 weeks otherwise) prior to the DCO date.

Additionally, summary statistics will be given for the number of days from censoring to DCO for all censored patients.

A summary of the duration of follow-up will be summarised using median time from randomisation to date of censoring (date last known to be non-progressor) in censored (not progressed) patients only, presented by treatment group.

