A forest plot illustrating the hazard ratio and the corresponding 95% confidence interval will be provided to compare the primary and sensitivity analyses of progression free survival.

The effect of covariates upon the HR estimate and the consistency of treatment effect between subgroups will be analysed for PFS using the same methods as those described for OS.

A further analysis of PFS (using investigator assessed RECIST) may be performed at the time of the OS analyses, if requested by health authorities.

Time to first subsequent therapy or death (TFST)

For supportive purposes, the time to the start of subsequent therapy will be analysed using the same methodology and model as that used for the co-primary analysis of PFS. The HR for the treatment effect together with its 95% CI will be presented. In addition, a Kaplan-Meier plot of the time to the start of subsequent therapy will be presented by treatment arm and the time between progression and starting subsequent therapy will be assessed based upon the investigator data defined date of progression. This will be summarised per treatment arm but no formal comparisons will be made. No multiplicity adjustment will be applied as this is viewed as a supportive endpoint.

In patients who received a subsequent cancer therapy, a summary table of first subsequent cancer therapies by treatment arm will be provided.

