4.2.2.6 Time from randomisation to second progression (PFS2)

Time from randomisation to second progression (PFS2) will be analysed using the same methods as outlined for the analysis of PFS and adjusting for the same set of covariates, but no subgroup analysis will be performed. Medians and Kaplan-Meier plots will be presented to support the analysis. The sensitivity analysis outlined in Section 4.2.1.2 will not be repeated for PFS2 with the exception of a Kaplan-Meier plot of the time to censoring where the censoring indicator of PFS2 is reversed.

The number and percentage of subjects experiencing a PFS2 event and the type of progression (objective progression by RECIST, symptomatic progression, new or worsening of soft tissue/visceral or bone metastases or other) will also be summarised by treatment arm.

Time to second subsequent therapy or death (TSST)

For supportive purposes, the time to the start of second subsequent therapy will be analysed using the same methodology and model as that used for the analysis of PFS2. The HR for the treatment effect together with its 95% CI will be presented. In addition, a Kaplan-Meier plot of the time to the start of second subsequent therapy will be presented by treatment arm and the time between progression and starting second subsequent therapy will be assessed based upon the site investigator data defined date of progression. This will be summarised per treatment arm but no formal comparisons will be made. No multiplicity adjustment will be applied as this is viewed as a supportive endpoint.

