5.1.1 PFS interim analysis

Approximately 367 PFS events (52% maturity) will be available for the interim PFS analysis.

The Lan DeMets spending function that approximates an O'Brien Fleming approach will be used to account for multiplicity introduced by including an interim analysis for superiority (Lan and DeMets 1983).

The criterion for superiority is a statistically significant improvement in PFS at the interim analysis. If 80% of the PFS events required at the time of the primary PFS analysis is available at the time of the interim (i.e., 367/458 PFS events have occurred), the 2-sided significance level to be applied for the PFS interim analysis would be 1.04% and the 2-sided significance level to be applied for the primary PFS analysis would be 2.19%.

PFS will be analysed using a stratified log-rank test (see Section 4.2.1.2 for details). However subgroup, sensitivity, secondary analysis and the global interaction test will not be performed at the interim. The hazard ratio will be estimated with corresponding CI and p-value. The size of the CI will be determined based on the actual number of events included in the interim analysis.

The progression status of patients at the time of the interim analysis will be summarised. A Kaplan-Meier plot of PFS will be presented by randomised treatment group, along with median PFS. The number of progression events will be presented by randomised treatment group.

If the PFS results indicate superiority, then analyses of all other endpoints may also be performed. Patients would continue to be followed for PFS and survival until approximately 458 PFS events, when the primary PFS analysis and the first interim OS analysis would be performed.

If the PFS interim analysis result does not meet the criterion of stopping for superiority, then all patients will remain blinded and continue to be followed for PFS and OS.

The recommendations from the IDMC will not reveal the results of the analysis but will take the form of "Continue/Modify/Stop".

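### The co-primary HR is estimated as exp(U/V); under 2:1 allocation this favours MEDI4736 by about 2–3% at the design effects, and its CI under-covers

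*SAP*

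**What the plan says.** SAP 4.2.1.1 takes the OS p-value from a stratified log-rank test and describes the treatment effect by the HR "together with its corresponding (1-alpha adjusted)% CI and p-value for the ITT population". On how to obtain them it states "The HR and CI can be estimated from the stratified log-rank as follows" and prints HR = exp(U/V) with limits exp(U/V ± 1.96/√V). U is observed minus expected events in one arm and V is its log-rank variance, both summed over strata. Protocol 12.2.2.1 prints the same formula.

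PFS "will be analysed by stratified log-rank tests, the same methodology as described for the OS analyses" (SAP 4.2.1.2). For the PFS interim, "The size of the CI will be determined based on the actual number of events included in the interim analysis" (SAP 5.1.1). Other endpoints inherit the method:

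- TFST is "analysed using the same methodology and model as that used for the co-primary analysis of PFS".
- PFS2 "will be analysed using the same methods as outlined for the analysis of PFS and adjusting for the same set of covariates", and TSST follows PFS2.
- TTDM follows PFS (SAP 4.2.2.7).
- The PRO time-to-deterioration endpoints follow OS (SAP 4.2.3.1 and 4.2.3.2).

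A Cox analysis is planned as an additional analysis: "A model will be constructed, containing treatment and the stratification factors alone", and "The result from the initial model and the model containing additional covariates will be presented". SAP 4.2.1.2 extends it to PFS. Neither document makes it the source of the headline HR. Allocation is 2:1 (SAP 1.2).

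**The concern.** U/V is a single step from log HR = 0, and V is the variance under the null. With equal arms the error of that step is negligible at moderate effects. With two thirds or more of the patients at risk on MEDI4736 it is not: the estimate overshoots towards the larger arm's benefit. 1/√V also understates how much the estimator varies. Labelling the other arm as Group 1 changes nothing, because U changes sign and V does not.

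The headline HR and CI for both co-primary endpoints would therefore overstate the benefit on average, and most CIs that miss would lie wholly below the true HR. SAP 5.1.2 makes the analyses that follow a superiority result the basis for regulatory submission, so a predictable error in the sponsor's favour matters even though it is small.

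**Working it through.** **Inputs (SAP 1.2 and 1.3).** 702 patients, 2:1; PFS HR 0.67 with 458 events; OS HR 0.73 with 491 deaths; two-sided 2.5% for each endpoint; placebo medians 10 and 22 months, exponential; 22 months' recruitment. The documents do not give stratum sizes, stratum hazards, accrual pattern or drop-out, so these are assumptions.

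**Step 1: reproduce the plan's figures.** Power = Φ(|ln HR|·√(2d/9) − 2.2414).

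- PFS: 0.4005 × 10.089 − 2.2414 = 1.799, which is 96.4% (plan: at least 95%).
- OS: 0.3147 × 10.446 − 2.2414 = 1.046, which is 85.2% (plan: at least 85%).
- Smallest significant HR: exp(−2.2414/10.089) = 0.801 and exp(−2.2414/10.446) = 0.807 (plan: 0.8 and 0.81).

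The inputs are read correctly.

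**Step 2: closed form.** Let p be the share of the risk set on MEDI4736 and t the true HR. Per event, U has expectation pt/(1 − p + pt) − p and V is p(1 − p). Hence U/V tends to (t − 1)/(1 − p + pt).

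- t = 0.67, p = 2/3: −0.33/0.78 = −0.423, so HR 0.655.
- t = 0.73, p = 2/3: −0.27/0.82 = −0.329, so HR 0.719.
- p = 1/2: 0.674 and 0.732, almost no error.

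No stratum assumption is needed. The MEDI4736 share rises as placebo patients have events faster. At p = 0.72 the values are 0.649 and 0.715.

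**Step 3: simulation.** 10,000 trials per scenario, randomised in blocks within eight strata, with exponential times, uniform accrual, a cut at the planned event count and no drop-out. Monte Carlo error of coverage is about 0.2 points.

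| Scenario | exp(U/V) centre | 97.5% CI coverage | Stratified Cox |
|---|---|---|---|
| PFS, true 0.67, 2:1 | 0.649 | 95.0% | 0.669, 97.4% |
| OS, true 0.73, 2:1 | 0.716 | 96.2% | 0.730, 97.5% |
| PFS, true 0.80, 2:1 | 0.791 | 96.6% | |
| OS, true 0.80, 2:1 | 0.792 | 96.9% | |
| PFS, true 0.67, 1:1 | 0.668 | 97.3% | |
| OS, true 0.73, 1:1 | 0.728 | 97.6% | |
| True HR 1, 2:1 | 0.999 | 97.6% | |

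- For PFS the upper limit falls below the truth in 4.1% of trials and the lower limit lies above it in 0.95% (nominal 1.25% each).
- Mean 1/√V against the actual SD of U/V: 0.1037 against 0.1134 (PFS), 0.0993 against 0.1055 (OS).
- Bias in SD units: ln(0.67/0.649)/0.1134 = 0.28 (PFS); ln(0.73/0.716)/0.1055 = 0.18 (OS).
- At the adjusted final levels, the 97.81% CI for PFS covers 95.5% and the 97.83% CI for OS covers 96.6%.
- At the 367-event PFS interim the centre is 0.651 and the 98.96% CI covers 97.9%.

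**Step 4: robustness.** For PFS, one stratum, eight equal strata or 1% monthly drop-out give 0.649–0.650 and 95.4–95.6% coverage. A separately programmed unstratified simulation (40,000 PFS and 30,000 OS trials) gives 0.649 with 95.4% and 0.715 with 96.1%; Cox on the same data gives 0.670 and 0.730, each with 97.5%.

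**The case against.** **No decision changes.** This is right. There is no bias at HR = 1, and with the adjusted z this CI excludes 1 exactly when the log-rank test is significant. A Cox CI gives up that exact match.

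**The shift is small, and a Cox result will be shown anyway.** Both are true, and they keep this a reporting defect. But the planned Cox model is supportive, so the headline remains the biased figure, and the two HRs will differ systematically. The subgroup forest plot would also set Cox HRs beside an exp(U/V) overall HR.

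**The wording is permissive.** SAP 4.2.1.1 says only that the HR can be obtained this way, and it mentions Breslow tie handling, which belongs to partial likelihood and not to the printed formula. So the size given here is conditional on the formula being used. No other estimator is named for the headline, however, and an open choice would itself need closing.

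**Cox is sensitive to ties.** PFS times were grouped exactly on the visit schedule, with 15% of events assumed to be deaths dated to the day. Breslow Cox then gave 0.681 and Efron 0.670 for a true 0.67. With visits scattered by ±7 days they gave 0.672 and 0.671. exp(U/V) stayed low (0.639 and 0.650). Tie handling should be specified, but it does not rescue the formula.

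**Hazards may not be proportional.** With an assumed 3-month delay in effect, exp(U/V) gave 0.741 and Cox 0.753. The gap narrows to about 1.6%, and neither estimates a single true HR.

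**Conclusion.** The concern holds. If the printed formula is used, the reported HR is on average about 3% too low for PFS and 2% too low for OS at the design effects. The 97.5% CI misses the truth in about 5.0% and 3.8% of trials instead of 2.5%, mostly by lying wholly below it. The error shrinks to about 1% at a true HR of 0.80. It grows with stronger effects: a true 0.50, outside the planning assumptions, gave 0.455 with 88.5% coverage. The direction and approximate size of the bias follow from the allocation ratio and design HRs alone. The exact figures rest on proportional hazards, uniform accrual and the assumed strata, and they barely moved when strata and drop-out were varied. No size was computed for the inheriting secondary and PRO endpoints. Testing, type I error, alpha spending and the success rule stand. The estimator should be changed, but the validity of the trial is not in question.

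**What to change.** Keep the stratified log-rank test for the p-value and state that it governs. Report the HR and CI for OS, PFS and the inheriting endpoints from a Cox model stratified by age, sex and smoking history (IVRS values). Use Efron ties, as SAP 4.2.1.1 already does for subgroups. Name one CI type, Wald or profile-likelihood, at the level set by each analysis's adjusted alpha. exp(U/V) can stay as a sensitivity estimate. Amend Protocol 12.2.2.1 to match.

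Editorially, the formula is labelled 95% and uses 1.96, although the SAP text requires an alpha-adjusted interval. Wherever the formula is kept, replace 1.96 by 2.292 (2.19%) or 2.296 (2.17%).

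The programming cost is one PROC PHREG call with a STRATA statement. The reported HR becomes less favourable by about 0.02 (PFS) and 0.014 (OS) on average at the design effects. The Wald CI and the log-rank decision disagreed in 0.04% of simulated trials (PFS, 0.67), 0.09% (OS, 0.73) and at most 0.33% (PFS, 0.80). Subgroup HRs stay unstratified, so the forest plot still mixes stratified and unstratified estimates. The protocol synopsis records that the planned analyses had concluded by Amendment 07. For results already reported, the stratified Cox estimate should therefore be added beside the planned one and labelled as post hoc.
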